# Participants:

- Do not complete the full study (e.g., due to experimenter or technical error, or missing surveys);
- Take too long to complete the study (|z| > 3 score on duration compared to the rest of the sample);
- Complete the follow-up survey later than 8 days after the study;
- Fail at least 2 attention/comprehension checks embedded into the study;
- Have an extreme score (|z| > 3) on any of the ratings AND suggest an explanation for this when asked (e.g., important life event leading to increase/decrease in symptoms; distraction during the testing procedure) OR express suspicion about the crucial points of the study (e.g., the real purpose of the study) when probed.

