# Primary hypotheses.

- I. Healthy participants who learn about symptoms of undiagnosed ADHD in adults will report higher rates of those symptoms and a higher rate of self-diagnosis with ADHD than healthy participants learning neutral information (control group).
- II. Participants who learn about nocebo effects at the same time as learning about ADHD will have fewer symptoms and lower rate of self-diagnosis after watching the videos compared to the ADHD group.

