# Dependent variables (primary outcomes).

- a. Inattentive ADHD symptoms, as measured by the subscale of Adult ADHD Self-Report Scale (ASRS)
- b. Hyperactive ADHD symptoms, as measured by the subscale of Adult ADHD Self-Report Scale (ASRS)
- c. ADHD self-diagnosis, as measured by an item on a 5-point Likert scale

**Study conditions**. We will test participants in groups. We will use block randomization (1:1:1) and assign each participant group to one of the three conditions:

- d. ADHD group
- e. ADHD + Nocebo education group
- f. Control group

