#### **Statistical Analysis Plan**

**Primary analyses.** We will use a mixed-effects model to predict each outcome variable outlined in the measures given the condition (ADHD, ADHD + nocebo, control) at one-week follow-up, with the covariate of baseline symptoms, as well as a random intercept for each participant (and group in which they were tested). We will use Tukey's test to compare all pairs of means for each outcome.

We will run directional tests and use Type I error rate of 0.05 for all the tests without correcting for family-wise error given the small number of tests.

**Secondary analyses.** If the sample is adequately powered, will also run subgroup analyses on the dependent variables based on participants' gender.

**Data exclusions.** We will exclude participant data points before computing statistical analyses if one of the following conditions is met.

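### The duration exclusion is worded one-sided but set two-sided, and its z score is pooled over three conditions that receive different material

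*Combined protocol and SAP*

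**What the plan says.** Under Data exclusions in the Statistical Analysis Plan, the rule is set out as "We will exclude participant data points before computing statistical analyses if one of the following conditions is met". The second item in the list that follows covers those who "Take too long to complete the study (|z| > 3 score on duration compared to the rest of the sample"). The reference for the z score is therefore "duration compared to the rest of the sample". The plan mentions no standardisation within condition, no transformation, and no definition of which interval is timed (the session alone, or the session plus follow-up).

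The conditions differ in content. Under Primary hypotheses, one arm learns about ADHD, the control arm receives neutral information, and a third consists of "Participants who learn about nocebo effects at the same time as learning about ADHD". Study conditions lists this third arm as "ADHD + Nocebo education group". The material is shown as videos whose lengths are not stated.

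Study conditions also says "We will test participants in groups" and "We will use block randomization (1:1:1) and assign each participant group to one of the three conditions", so every member of a session belongs to the same arm.

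**The concern.** Two features of the bullet need attention.

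- **Direction.** The wording is one-sided and the threshold is two-sided. Two analysts could treat a very fast completer differently, which a pre-specified rule should prevent.
- **Reference group.** This exclusion is applied after randomisation and before analysis. If one condition's session runs longer, its members get higher z scores because of what they were assigned to watch. The rule then removes more of that arm, including in the ADHD versus ADHD + Nocebo comparison of the second hypothesis.

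Group testing adds a related risk. A session held up for logistical reasons raises the duration of all its members at once, and any resulting loss falls on a single arm.

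**Working it through.** The plan gives no sample size, duration or exclusion rate, so there is no figure of its own to reproduce. The following are assumptions: 100 per arm, lognormal durations with log-SD s = 0.4, and one arm longer by a fraction d of the mean duration. That z is taken on untransformed time is inferred from the plan's silence. Times below are in units of the mean duration in a shorter arm.

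**1. Equal lengths.** The coefficient of variation is √(exp(s²) − 1) = √0.1735 = 0.4165.
- The upper cut is 1 + 3 × 0.4165 = 2.25. The lognormal mean is exp(s²/2) = 1.0833, so the fraction above the cut is P(Z > ln(2.25 × 1.0833)/0.4) = P(Z > 2.23) = 1.3% in each arm.
- The lower cut is 1 − 3 × 0.4165 = −0.25. No duration can fall below it, so under this assumption z > 3 and |z| > 3 remove the same people. With symmetric durations each tail would hold 0.135%, and the two readings would differ.

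**2. One arm longer, d = 0.30, extra time added.** The pooled mean is 1 + 0.30/3 = 1.10. The pooled variance is 0.1735 + 2d²/9 = 0.1735 + 0.0200 = 0.1935 (SD 0.440). The cut is 1.10 + 3 × 0.440 = 2.42.
- Each shorter arm: P(Z > ln(2.42 × 1.0833)/0.4) = P(Z > 2.41) = 0.8%.
- Longer arm: P(Z > ln((2.42 − 0.30) × 1.0833)/0.4) = P(Z > 2.08) = 1.9%.

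**3. Same d, every duration in that arm multiplied by 1.30.** The pooled variance is 0.1735 × (1 + 1 + 1.69)/3 + 0.0200 = 0.2334 (SD 0.483), and the cut is 2.55.
- Each shorter arm: P(Z > 2.54) = about 0.55%.
- Longer arm: P(Z > 1.88) = 3.0%.

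**4. Simulation of 3 × 100 participants**, excluded in the longer arm against each other arm:

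| Extra time | Additive | Proportional |
|---|---|---|
| 15% | 1.6% vs 1.1% | 2.1% vs 0.9% |
| 30% | 1.9% vs 0.8% | 3.0% vs 0.5% |
| 50% | 2.0% vs 0.5% | 3.8% vs 0.3% |

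For 30% extra at log-SD 0.6, the additive result is 2.2% vs 1.4% and the proportional result 3.1% vs 1.1%. At log-SD 0.25 the proportional result is 2.5% vs 0.13%. With z computed within condition at log-SD 0.4, about 1.2% is excluded from each arm in every scenario.

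**5. Effect on a contrast.** Suppose excluded participants differ from the rest of their arm by a full outcome SD (assumed). The shift is then roughly the difference in exclusion rates. At 30% this is 0.019 − 0.008 = 0.011 SD (additive) or 0.030 − 0.005 = 0.025 SD (proportional). The largest row gives 0.038 − 0.003 = 0.035 SD. For comparison, the standard error at 100 per arm, ignoring clustering and the baseline covariate, is √(2/100) = 0.14 SD.

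**6. Delayed session.** If k of n participants share a delay and there is no other spread, their z is √((n − k)/k).
- A whole arm (100 of 300) reaches only √2 = 1.41, so an arm offset alone cannot remove an arm.
- A session of 10 among 300 (assumed size) reaches √29 = 5.4. When such a session is delayed by one mean duration, simulation puts 98%, 52% or 15% of its members above z = 3 at log-SD 0.15, 0.25 or 0.4.

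**The case against.** The strongest reply is that the harm is hypothetical. The arm names and hypotheses describe content, not running time, and the videos may be matched in length, in which case exclusions balance. Even with unequal lengths, the step 5 shifts are a fraction of a standard error. The direction conflict may also have no effect, since under right-skewed durations the lower tail is empty. All of this stands and limits the size of the point. It does not remove the contradictory wording or justify a pooled reference.

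Three stronger readings are tempting, and the documents do not support them.

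- **That the rule removes mainly the longer arm, at many times the rate of the others.** No length difference is stated. The largest ratios also come from multiplying every duration, whereas a longer video more naturally adds a fixed amount. At 50% extra, the additive ratio is about 4, against roughly 15 when proportional.
- **That careless fast responders stay in.** The bullet's words aim at slowness. The same list separately excludes anyone who fails at least two attention or comprehension checks, which partly covers rushing.
- **That log time, median absolute deviations or page-level timing are needed.** These are preferences. At log-SD 0.4, a within-condition log rule would cut upper-tail exclusions from about 1.3% to about 0.1%, which is a substantial change to the rule.

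**Conclusion.** The point holds in a limited form. Two parts rest on the text alone: the wording and threshold disagree on direction, and z is pooled over conditions that receive different material. Unequal exclusion is conditional on a difference in session length that the plan does not state. Given such a difference, the excess is about 0.5 to 3.5 percentage points of one arm across the log-SD 0.4 scenarios, and the effect on the primary contrast is probably small. Losing much of a delayed session is possible when individual spread is small or the delay is long. How likely that is cannot be judged, because group size, pacing and the timed interval are not given. This is a clarification worth making because it costs so little. It is not evidence that the primary comparison is biased.

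**What to change.** Replace the bullet with: *Duration too long: z > 3, with z computed among participants in the same condition.* If fast completers are also meant to go, keep |z| > 3 and word it as too long or too short.

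In the same edit, name the interval that is timed. Report the number excluded under this rule by arm, and add a sensitivity analysis that keeps these participants.

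The cost is one sentence, slightly noisier cut-offs from smaller reference groups, and one extra analysis. Within-condition z does not fully solve the delayed-session problem, although it lessens it: by the step 6 formula, 10 of 100 gives √(90/10) = 3 in place of 5.4. Naming the interval and reporting by arm will show whether it occurred. Log transformation, median absolute deviations and page-level timing are optional.

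### The extreme-and-explained exclusion is not limited to baseline, so a follow-up primary outcome can decide who is analysed, and no analysis without the rule is planned

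*Combined protocol and SAP*

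**What the plan says.** The Data exclusions paragraph of the Statistical Analysis Plan states: "We will exclude participant data points before computing statistical analyses if one of the following conditions is met". The list that follows, under Participants, removes those who "Have an extreme score (|z| > 3) on any of the ratings AND suggest an explanation for this when asked". The examples of a qualifying explanation are "important life event leading to increase/decrease in symptoms; distraction during the testing procedure". No time point is attached to the ratings.

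The primary model uses the outcomes "at one-week follow-up, with the covariate of baseline symptoms". Two outcomes are ASRS subscales. The third is "ADHD self-diagnosis, as measured by an item on a 5-point Likert scale". Primary hypothesis I is that the ADHD group "will report higher rates of those symptoms and a higher rate of self-diagnosis with ADHD".

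A reference set for z appears only in the duration bullet: "score on duration compared to the rest of the sample". The only other analysis named is by gender. The documents do not say who asks for or judges the explanation, or whether that person knows the condition. The same bullet also has a suspicion clause, which is not part of this point.

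**The concern.** All three primary outcomes are self-reported ratings taken after assignment, so they fall within the rule as worded. The example of a life event that changes symptoms also points to change after baseline. If condition raises these scores, the ADHD arm should contain more extreme scorers than control. Whether such a person then offers an explanation is itself a response given after exposure, and the arms have been taught different things about symptoms and expectations. Selection can therefore depend on both outcome and arm, and randomisation does not protect against that.

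Non-completion, duration, late follow-up and failed checks also act after assignment, but none of them selects on the value of a rating. At stake are the ADHD versus control and ADHD versus ADHD + nocebo contrasts, above all on the self-diagnosis item. A five-point item with most answers at the bottom is where |z| > 3 is easily reached.

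**Working it through.** The documents give no sample size, effect size, SD or expected exclusion rate, so there is no stated figure to reproduce. What follows is an illustration. From the plan: |z| > 3, 1:1:1 allocation and a five-point item. Assumed: all shares, explanation rates, shifts and correlations. The figures are unadjusted arm means, not output of the planned mixed model.

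**1. Floor-skewed item, pooled z.** Assumed shares at scores 1 to 5:
- ADHD .66/.19/.08/.05/.02, mean 1.580
- ADHD + nocebo .75/.165/.05/.025/.01, mean 1.380
- Control .80/.13/.05/.015/.005, mean 1.295

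ADHD minus control = 1.580 − 1.295 = 0.285. The pooled mean is 1.418 and the SD 0.827, so z(4) = (4 − 1.418)/0.827 = 3.12, z(5) = 4.33 and z(3) = 1.91. Scores 4 and 5 are flagged: 7.0%, 3.5% and 2.0% of the three arms. Mean after exclusion = (mean − Σ removed share × score)/(1 − removed share).

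*Only background scorers explain* (closest to the plan's examples). The control arm's flagged share leaves every arm, so the same quantity leaves each numerator and denominator:
- half of them: 0.285/0.99 = 0.288 (+1%)
- all of them: 0.285/0.98 = 0.291 (+2%)

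*Half of all flagged scorers explain, equally in every arm:*
- ADHD: (1.580 − 0.025×4 − 0.010×5)/0.965 = 1.482
- Control: (1.295 − 0.0075×4 − 0.0025×5)/0.990 = 1.265
- Difference 0.217 (−24%)

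*Standardised by the root-mean-square within-arm SD:*
- all kept: 0.285/0.818 = 0.348
- half explain: 0.217/0.713 = 0.304 (−13%)
- background only: 0.288/0.769 = 0.374 and 0.291/0.715 = 0.407

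**2. The z reference matters.** In the same half-explain case with z taken within arm, a 4 is extreme in control (z = 4.00) but not in ADHD (z = 2.49). ADHD becomes (1.580 − 0.010×5)/0.990 = 1.545, control is again 1.265, and the difference is 0.280. Standardised, it is 0.376, above the 0.348 with all kept.

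**3. No true effect.** Shares .74/.16/.06/.03/.01 in every arm; mean 1.41, z(4) = 3.18.
- 25% of flagged explain: (1.41 − 0.0075×4 − 0.0025×5)/0.99 = 1.381
- 75% explain: (1.41 − 0.0225×4 − 0.0075×5)/0.97 = 1.322
- False difference 0.059, with its sign set by which arm explains more. Equal rates give zero.

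**4. Flat item.** Shares .35/.27/.20/.12/.06, .42/.28/.17/.09/.04 and .45/.28/.16/.08/.03 give a pooled mean of 2.093 and SD of 1.162. Then z(5) = 2.50, so nobody is flagged and nothing changes.

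**5. ASRS subscales.** Assumed shifts are 0.3/0.15/0 SD, pooled z, half of flagged explain, 3 million simulated scores per arm.
- Flagged on their own score: the ADHD minus control shift changes by −1.3% (normal), −2.2% (gamma, skewness 1) or −2.7% (gamma, skewness 2).
- Flagged on the floor-case self-diagnosis item and dropped from every analysis: take a latent normal behind the item, correlated 0.5 with ASRS. The mean latent score is 1.918 in the top 7% and 2.421 in the top 2%. The shift becomes 0.3 − 0.5×(0.035×1.918/0.965 − 0.010×2.421/0.990) = 0.277, or −7.5%. At correlations of 0.3 and 0.7 it is −4.5% and −10.5%.

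**The case against.** The best defence is that the rule is narrow and mostly clear. It needs an extreme score and an explanation together, so a high score alone excludes nobody. Both examples are causes unrelated to the intervention, and in the case closest to them, with pooled z, the contrast moves by only 1% to 2%. Removing such people also removes noise. The words used for the ratings are broad rather than undefined. Participants is the subject of every bullet, which makes removal of the whole person the natural reading. The duration bullet makes whole-sample z the likely intention. All of this stands, and the within-arm figure above belongs to the less natural reading.

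Three further cautions also stand. Raw percentages overstate the change, because exclusion shrinks the SD as well (−24% raw is −13% standardised). A larger standardised difference is not evidence of less bias. The illustration leaves out the baseline covariate and the random intercepts.

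What the defence does not remove is that the rule as written covers follow-up outcomes, that offering an explanation is a post-exposure response that may differ by arm, and that no analysis without the rule is planned. Specifying an exclusion in advance does not make it independent of the outcome.

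**Conclusion.** The point holds as a defect of design and reporting, not as a demonstrated bias. It is certain from the text that the rule can select on a primary outcome and that nothing planned would reveal the result. The size is unknown. On a floor-skewed item with pooled z, it runs from +1% to +2% (background scorers only) to −24% raw (half of all flagged explain), with a possible false difference of about 0.06 if explaining differs by arm. It is zero on a flat item. ASRS scores are barely affected by their own extremes. The larger ASRS change needs a floor-skewed item, treatment-driven scorers who explain, and an assumed correlation.

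A reader might infer that the rule will weaken the ADHD effect, or inflate it. The documents support neither, because they give no score distribution and no explanation rates. A reader might also infer that the plan leaves open which ratings count and whether a person or a single value is dropped. Those are largely settled by natural reading; only the z reference for ratings is not stated. The change is worth making because it is cheap. Confidence is high on the text and low on the size.

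**What to change.** Do not let follow-up outcome values decide inclusion in the primary analysis. Either limit the extreme-and-explained rule to baseline ratings, or keep it as a sensitivity analysis. At minimum, pre-specify one analysis of everyone with a follow-up score, reported beside the planned one. In the same paragraph, state the set over which z is computed and that the person is removed. Decide exclusions blind to condition, and report counts by arm and reason.

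The cost is a few lines of SAP text and one extra model run per outcome. Some noisy scores stay in. In the illustrated pooled-z cases where only background scorers would have been removed, keeping everyone lowers the standardised difference by about 7% (1 − 0.3484/0.3742) to 14% (1 − 0.3484/0.4066). Where half of all flagged scorers explain equally, keeping everyone gives the larger standardised difference with pooled z (0.348 against 0.304) and the smaller one with within-arm z (0.348 against 0.376).

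### All analyses follow exclusions that can arise after assignment and may depend on arm or outcome; no all-assigned sensitivity analysis is named, and the last exclusion rule is ambiguous.

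*Combined protocol and SAP*

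**What the plan says.** The Data exclusions paragraph of the Statistical Analysis Plan reads: "We will exclude participant data points before computing statistical analyses if one of the following conditions is met". No analysis is exempt. The only analyses described are the mixed model at one week with pairwise comparisons, and a gender subgroup analysis that depends on adequate power.

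The list under Participants has five bullets:
- non-completion: "Do not complete the full study (e.g., due to experimenter or technical error, or missing surveys"
- an extreme study duration relative to the other participants
- a follow-up survey returned after more than 8 days
- two or more failed checks of attention or comprehension
- a combined rule on ratings and suspicion. It begins "Have an extreme score (|z| > 3) on any of the ratings AND suggest an explanation for this when asked", gives examples in parentheses, and then adds a further ground: "OR express suspicion about the crucial points of the study (e.g., the real purpose of the study) when probed"

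On testing, the plan says "We will run directional tests and use Type I error rate of 0.05 for all the tests without correcting for family-wise error". It also plans Tukey's test "to compare all pairs of means for each outcome". Baseline symptoms are a covariate. Conditions are assigned by block randomisation to groups of participants. The text supplied for review names no all-assigned set and no sensitivity analysis.

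**The concern.** Randomisation makes the arms comparable as assigned, not as filtered afterwards. All five bullets can be met after assignment, and late follow-up can only be met then. Two of them deserve particular attention.

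- **Extreme score with an explanation.** It covers every rating, with no limit to baseline. One of the plan's own examples is a life event that raised or lowered symptoms, so follow-up outcome scores appear to be in scope.
- **Suspicion of the purpose.** The nocebo education teaches about the role of expectations, which is close to what a probe about the study's purpose would touch. Suspicion could therefore be more common in that arm. Comprehension checks could also differ with video content. Both are possibilities only, because neither the probe wording nor the checks are given.

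If exclusion differs by arm and is related to follow-up symptoms beyond what baseline explains, the planned contrasts are biased, most plausibly for hypothesis II. The plan has no analysis that would show it.

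The last bullet also has the form A AND B OR C. Its parentheses hold only the threshold and examples, so nothing groups the logic. Two analysts could build different samples from it.

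**Working it through.** The documents give no sample size, SD or exclusion rate, so there is no planned figure to reproduce. Everything numerical below is an illustration on assumed inputs.

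**1. The two readings of the last bullet.** Let A be |z| > 3 on any rating, B an explanation, C suspicion. Assume 300 participants, 3 independent normal ratings, P(B) = 0.5, and A, B and C independent.
- P(A) = 1 − (1 − 0.0027)³ = 0.0081.
- (A AND B) OR C, with P(C) = 0.10: 1 − (1 − 0.0081 × 0.5)(1 − 0.10) = 0.104, about 31 people. With P(C) = 0.05 or 0.20 it is about 16 or 61.
- A AND (B OR C), with P(C) = 0.10: 0.0081 × (1 − 0.5 × 0.9) = 0.0045, about 1 person. The result is about 1 at the other rates too.

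**2. Bias in the ADHD versus nocebo-education contrast.** Assume that suspicion alone excludes, that education has no true effect, and that those removed have more symptoms. A standard normal selection variable U is kept below its (1 − p) quantile, with p = 0.10 in the ADHD arm and 0.30 in the education arm. Assume also:
- correlation of U with symptoms, ρ = 0.2 to 0.3
- baseline to follow-up correlation, r = 0.5 to 0.7
- 60 or 100 assigned per arm, participants independent

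The mean of U among those kept is −φ(z)/(1 − p): −0.195 in the ADHD arm and −0.497 in the education arm. The difference is D = 0.302. Without a covariate the bias would be ρD, that is 0.2 × 0.302 = 0.060 to 0.3 × 0.302 = 0.091 SD. That is not the planned model. With the baseline covariate the bias is close to the expressions below; the ranges use exact truncated moments.

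| How selection acts | Approximate bias | Range, SD | One-sided 5%, uncorrected | Tukey critical value |
|---|---|---|---|---|
| Through follow-up | ρ(1 − r²)D | 0.031–0.069 | 7.6–12.7% | 1.6–3.2% |
| Equally on both | ρ(1 − r)D | 0.018–0.047 | 6.4–9.6% | 1.3–2.2% |
| Through baseline only | 0 | 0 | 5.0% | 0.9% |

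Worked cell: ρ = 0.3, r = 0.5, 100 per arm, selection through follow-up. The approximation is 0.3 × 0.75 × 0.302 = 0.068, and the exact value is 0.0685. With 90 and 70 kept, the standard error is 0.136, so the shift is 0.0685/0.136 = 0.50. One-sided error is 1 − Φ(1.645 − 0.50) = 12.7%. With the Tukey critical value of 2.358 it is 1 − Φ(2.358 − 0.50) = 3.2%.

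Smaller imbalances, covariate-adjusted:
- 10% versus 20% removed: 0 to 0.035 SD, one-sided error 5 to 8.4%, Tukey 0.9 to 1.8%.
- 10% versus 15% removed: 0 to 0.018 SD, one-sided error 5 to 6.6%, Tukey 0.9 to 1.3%.

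If those removed have fewer symptoms instead, for example because the education worked in them, the sign reverses. At 10% versus 30% the adjusted one-sided error is then about 2 to 5%.

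**3. Explained extreme scores on the five-point item.** Assume percentages at ratings 1 to 5 of 62/22/8/5/3 (ADHD), 70/18/7/3.5/1.5 (education) and 76/15/6/2/1 (control), with z computed over the pooled arms. Then z = 2.76 at rating 4 and 3.86 at rating 5, so only rating 5 is extreme. The ADHD minus control difference is 1.65 − 1.37 = 0.28. If half of those at rating 5 are removed, it becomes (1.65 − 0.075)/0.985 − (1.37 − 0.025)/0.995 = 0.247. If a quarter are removed, it is 0.264. In a more skewed assumed set, where rating 4 is only just extreme (z = 3.07), 0.28 becomes 0.245 to 0.209. In a flatter set (50/25/13/8/4), rating 5 has z = 2.71 and nothing changes.

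**The case against.** Excluding inattentive or suspicious participants is a defensible aim in a study about expectations, and the rules are written in advance. That limits analyst discretion. It does not remove bias from selection after assignment, and the last bullet is not fully specified.

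The suspicion route depends on one reading. (A AND B) OR C follows the usual precedence of AND over OR. Yet suspicion shares a bullet with extreme scores while every other ground has its own, which favours A AND (B OR C). On that reading almost nobody is removed by the bullet. This stands: the figures in step 2 hold only if suspicion alone excludes.

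The baseline covariate removes the bias only if exclusion relates to follow-up solely through baseline symptoms. The symptom-change example suggests otherwise for the extreme-score rule.

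A reader might infer that the trial's false-positive rate rises to 9–14%. That range comes from the unadjusted calculation at 10% versus 30%, which is not the planned model, with an uncorrected test. With the Tukey critical value, error in the predicted direction stays below 5% in every scenario. The plan names both approaches, so neither is settled. Allowing for group testing would enlarge the standard errors and reduce the inflation.

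A reader might also infer that the exclusions favour the hypotheses. The documents do not support a direction: the suspicion effect can go either way, and trimming explained extremes tends to shrink the hypothesis I contrast.

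**Conclusion.** The gap in the text is firm. Exclusions that can follow assignment precede every analysis, at least one can act on the outcome, one may depend on arm content, and no named analysis would reveal the consequence. The ungrouped last bullet is a separate and equally firm defect. Absence is judged on the text supplied for review.

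The size of any bias is not established. On the stated assumptions, with suspicion alone excluding and the baseline covariate in the model, it runs from 0 to 0.07 SD at 10% versus 30% removed and is small at 10% versus 15%. Equal exclusion, with the same relation to symptoms in each arm, gives none. The documents do not show that the contrasts will be biased, nor that the all-assigned set must be primary. Because retained participants who guessed the purpose may bring demand effects that differ by arm, that choice is a genuine trade-off. The plan should be corrected before analysis because the remedy is cheap and a reader otherwise cannot tell whether exclusion affected the result.

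**What to change.** - Pre-specify, at least as a named sensitivity analysis reported beside the primary result, the same model in all assigned participants with an available follow-up score. Analyse them by the condition assigned to their session, keeping late, slow, suspicious, extreme-scoring and check-failing participants. Which set is primary may stay the sponsor's choice.
- Do not exclude on follow-up outcome values in the primary set. State which ratings and time points the |z| > 3 rule covers.
- Decide exclusions blind to arm as far as the responses allow.
- Report exclusions and missing follow-up scores by arm and reason. The added set still lacks participants with no follow-up score, so these counts matter.
- Put brackets in the last bullet.

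The cost is plan wording and one extra model per outcome, on data mostly already collected. The all-assigned set will carry some added noise, a less sharply defined one-week time point, and possible demand effects. Reporting the exclusion-based analysis alongside addresses these.
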